10.1 Evaluation: Simple reaction psychomotor test

The examined individual should sit in front of the monitor with the index finger of the dominant hand positioned on the sensor (called the "stand-by key") located on the control panel. The individual will be instructed to hold their finger on the "stand-by key" and move it to the "reaction key" as soon as the stimulus (yellow light) appears.

The tested parameters are:

A1 - median reaction time (interval between the start of a given stimulus and the release of the "stand by key", in ms):

A2 - median movement time,

A3 - median total response time.

10.2 Evaluation: Psychomotor test of reaction of choice

One individual was instructed to respond appropriately and as quickly as possible to stimuli appearing on the screen using the upper and lower limbs.

Five colored optical stimuli (white, yellow, blue, green, and red) in the form of a circle appeared on the screen, and each circle received its own "reaction key" on the control panel that corresponded to the color of the stimulus.

The examined individual was asked to respond to the stimulus by pressing the corresponding "reaction key" with the right or left hand, and the foot was also instructed to press the right or left pedal whenever a white rectangular light appeared on the black background of the screen. Finally, the test included reaction to acoustic stimuli.

The tested parameters are:

B1 - number of correct answers (n),

B2 - number of incorrect and missed answers (n),

B3 - median response time(s)

10.3 Collection of blood samples and analysis of biomarkers

In the blood collection will be collected samples of 8 ml of the cubital vein of the forearm of the patients according to the method used in Mendes et al. (2021). The samples will be stored in tubes containing ethylenediamine tetraacetic acid (EDTA) 10 or without anticoagulants. The serum should be acquired by the centrifugation method (1000 x g for 10 minutes at 4°C) and stored at – 80°C in polypropylene microcentrifuge tubes until analysis.

Pro-inflammatory biomarkers will contain acute phase proteins such as the cytokines TNF-alpha, IL-6, IL-1 beta, monocyte chemoattractant protein 1, and adhesion molecules. Anti-inflammatory markers: cytokines such as IL-10 and adiponectin that acts on muscles as anti-inflammatory cytokines (FANG et al., 2023).

The serum levels of the biomarkers will be determined by cytometry (flow cytometer FACSverse, BD Biosciences), using a commercial kit Cytometric Bead Array Human Inflammation kit, according to the manufacturer's instructions. Data will be analyzed using FCAP arrayTM (MENDES et al., 2021; SCHULZ et al., 2016)

Blood samples will be collected 1 hour before the high-intensity strength exercise, in the condition of muscle rest. From that moment the participants, randomly divided into two groups, will be selected to drink the extract of juçara (*Euterpe edulis*) or the placebo. New blood samples will be collected after the completion of the muscular effort, specifically 3 minutes after the exercise performed, in addition to the 3rd sample after 24 hours of rest.

Will be evaluated in the blood samples collected: plasma biomarkers, which include lactate concentration (LA). In plasma, creatine kinase (CK), total antioxidant capacity (TAC) and concentrations of testosterone (T), cortisol © and growth hormone (GH) will be analyzed. In addition to serum concentrations of inflammatory biomarkers such as interleukins (IL-6, IL-8, IL10) and TNF-alpha.

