[figure not shown]

Official Title: Effect of supplementation with *Euterpe edulis* on the physical and mental performance of healthy men submitted to physical exercises

Ethical committee Protocol No: 6.202.888

Study protocol

1. Type of study

This is a clinical study, double blind, with the purpose of offering the juice of *E. edulis*, daily for 4 weeks before the day of the final evaluation, compared to the control. There will be about 40 men, aged 19 to 30 years, who perform regular physical exercises, in total of 150 min per week, at a minimum of 3 months.

2. Experimental Protocol

The men will be randomized into two groups, called GJ who will receive the sample and GP who will receive the placebo. The sample consists of 250 mL of juçara juice and the placebo which is 250 mL of water with pectin and natural dye. Research subjects will maintain their exercise routine, as well as fill out a food diary that will be sent electronically. The research will be for 11 days, and on day 1 (D1) of the research he will have the blood collected. On day 11 of the D11 survey, at time zero he will have the blood collected, and then consume the sample or the placebo. Two hours after he will be subjected to the battery of exercises, following 1. Dorsal dynamometer, 2. shoulder dynamometer, 3. manual dynamometer, 4. ergospirometry + electrocardiogram + digital lactate, 5. jump test for 1 min (amounts of jumps), 6. Pollock abdominal test and 7. functional mobility test. At the end, the blood will be collected, and a psychological form will be applied. After 2 and 7 days of physical exercise will be applied visual pain test.

3. The size of the sample

The calculation of the sample of patients for this study was performed using the software G*Power3.1.9.7 (Public domain). Considering the alpha value equal to 0.05 and the power of test $1 - \beta$ as 95% (0.95, that is, determining that the probability of type II error (β) should not be greater than 5%), the value of 20 patients was reached.

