On day 11 of the D11 survey, at time zero he will have the blood collected, and then consume the sample or the placebo. Two hours after he will be subjected to the battery of exercises, following 1. Dorsal dynamometer, 2. shoulder dynamometer, 3. manual dynamometer, 4. ergospirometry + electrocardiogram + digital lactate, 5. jump test for 1 min (amounts of jumps), 6. Pollock abdominal test and 7. functional mobility test. At the end, the blood will be collected, and a psychological form will be applied. After 2 and 7 days of physical exercise will be applied visual pain test.

9. Preparation of Juçara juice

The preparation will be obtained with the same methods already well established in previous studies (SCHULZ et al., 2016.; MENDES et al., 2021). Participants will receive 250 ml of water + purple dye + pectin (control) or commercial samples of juçara (*E.edulis*) refrigerated to 4°C to 10°C, per day, for 10 days, and on the 11th will be the exercise and on this day will be administered the juice of the juçara 2 h before on the day of the monitored exercise. The chemical characterization of *Euterpe edulis* will be with at least 350.0 + or - 17.5 mg of total phenolics (gallic acid equivalent), 186.0 + or - 7.5 mg of total monomeric anthocyanins (cyanidin 3-glycoside), 0.73 + or less 0.01 g of proteins, and 2.75 + or - 0.03 g of lipids (ether extract). During the 10 days of previous treatment, maintain the routine of physical exercises.

10. Values evaluated

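### The sections conflict on supplementation period, drink timing and blood draws; no draw is stated to precede the first serving, and the reaction tests are not explicitly assigned to a visit

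*Combined protocol and SAP*

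**What the plan says.** **Supplementation period.** Section 1 has the juice given "daily for 4 weeks before the day of the final evaluation". Section 9 has it given "per day, for 10 days, and on the 11th will be the exercise", and adds "During the 10 days of previous treatment, maintain the routine of physical exercises". Section 2 states "The research will be for 11 days, and on day 1 (D1) of the research he will have the blood collected".

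**Test day.** Sections 2 and 8 use the same text: "On day 11 of the D11 survey, at time zero he will have the blood collected, and then consume the sample or the placebo", then "Two hours after he will be subjected to the battery of exercises". Section 9 agrees on the drink, placing it "2 h before on the day of the monitored exercise". Section 10.3 instead says "Blood samples will be collected 1 hour before the high-intensity strength exercise, in the condition of muscle rest", and has the randomised men take juice or placebo from that point.

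**Later draws.** Sections 2 and 8 have one draw when the battery ends. Section 10.3 has one 3 minutes after exercise and one after 24 hours of rest, which it numbers as the third sample.

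**Mental performance.** The title names it as an aim. Sections 10.1 and 10.2 describe two reaction tests with six parameters (A1 to A3, B1 to B3) and give no day or visit for either. The day-11 sequence lists seven physical items and then a psychological form. Section 10.6 describes a fatigue questionnaire still to be developed. A sentence in section 3, repeated after section 7, says that each man is assessed at the start and finish of exercise; it names no test.

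**Analysis.** Section 11 plans a one-way repeated-measures ANOVA with Tukey comparisons. It names no time points and no baseline.

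**The concern.** These instructions cannot all be followed. Staff working from section 10.3 would collect a different set of samples from staff working from section 2, and would give the test-day drink at a different interval before exercise. A sample or test that is not taken before supplementation cannot be obtained later.

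At stake is the content of the analysis. Change over the supplementation period needs the day-1 draw, which is only in section 2. Recovery at 24 hours needs the last draw, which is only in section 10.3. For reaction time, the plan leaves open whether it is measured before supplementation, before exercise or after exercise, although these tests are the only objective measures described for half of the title's aim.

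**Working it through.** The plan gives no calculated figure to reproduce on this point. The check sets the sections side by side and counts days and draws.

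| Item | Section 1 | Section 2 | Section 8 | Section 9 | Section 10.3 |
|---|---|---|---|---|---|
| Supplementation before the test day | 4 weeks | study lasts 11 days | – | 10 days | – |
| Drink to exercise | – | 2 h | 2 h | 2 h | at most about 1 h |
| Day-1 draw | – | yes | – | – | not listed |
| Pre-exercise draw | – | before the drink, about 2 h | before the drink, about 2 h | – | 1 h |
| Post-exercise draw | – | end of battery | end of battery | – | 3 min after |
| 24 h draw | – | not listed | not listed | – | yes, as third sample |

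**1. Period.** 4 weeks × 7 = 28 daily servings (section 1) against 10 (section 9). The ratio is 28 / 10 = 2.8. Twenty-eight days do not fit in an 11-day study.

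**2. Drink and pre-exercise draw.** If the drink is taken 2 h before exercise, a draw 1 h before exercise falls 2 − 1 = 1 h after the drink. Section 10.3 puts that draw before the drink. If the wording in 10.3 is taken to mean allocation to a group and not drinking, it conflicts with section 9 instead, because the men would already have had 10 days of juice or control. Either reading leaves a contradiction.

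**3. Draws.** There are four named occasions. One is compatible across sections (post-exercise), one conflicts (pre-exercise, about 2 h against 1 h), one is in section 2 only (day 1), and one is in 10.3 only (24 h). Since 10.3 numbers the 24 h sample third, its count has no place for day 1.

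**4. Does any draw precede the first serving?**
- Section 9 with section 2: the 10 servings before day 11 fall on days 1 to 10, so none precedes day 1. The first serving and the first draw share day 1, and their order is not stated.
- Section 9 with section 10.3: all three samples follow 10 days of servings, so there is no pre-supplementation sample.
- Section 1, on the assumption that the final evaluation is day 11: 10 of the 28 servings fall on days 1 to 10, and 28 − 10 = 18 precede day 1.

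**5. Reach.** The blood analytes named in 10.3 are TNF-alpha, IL-6, IL-1 beta, monocyte chemoattractant protein 1, IL-10, adiponectin, lactate, creatine kinase, total antioxidant capacity, testosterone, cortisol, growth hormone and IL-8. That is 13, plus unnamed adhesion molecules. Reaction tests explicitly assigned to a visit: 0 of 2.

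**The case against.** The best defence is that day 1 is plainly the baseline. It is a separate draw on the first day of an 11-day study, no section puts a serving ahead of it, and wherever the plan orders blood and drink on the test day, blood comes first. This is probably the intention, and a reader should not infer that the trial has no baseline. What remains is that the order on day 1 is nowhere stated and that the blood-collection section leaves day 1 out.

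A reader might also infer that 18 servings precede day 1. That joins section 1's 4 weeks to section 2's calendar, which are themselves in conflict; if 4 weeks were the true period, day 1 could be its first day. The figure is conditional only.

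A reader might infer that the group comparison is biased. It is not: the men are randomised, and the day-11 pre-exercise draw still allows the groups to be compared on their response to exercise.

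The general sentence on assessment around exercise may be meant to cover the reaction tests. It names neither test nor day and gives no measurement before supplementation, so it does not settle their timing. The psychological form could be the section 10.6 questionnaire. The plan does not link them, and 10.6 concentrates on physical fatigue.

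Some differences are not conflicts. Section 8 describes day 11 only, so its silence on day 1 contradicts nothing. The end-of-battery and 3-minute draws are compatible. A 24 h draw would fall on day 12, which is possible, since the pain tests at 2 and 7 days already fall on days 13 and 18. The different names for the abdominal and functional tests in sections 2 and 10.4 do not by themselves show different procedures.

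**Conclusion.** The point stands as a contradiction in the current text on three items: supplementation period (28 days against 10, in an 11-day study), test-day drink (2 h against at most about 1 h before exercise) and pre-exercise draw (about 2 h against 1 h). Two further draws each appear in one section only.

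No draw is certain to precede the first serving, and sections 9 and 10.3 followed together leave none that does. The reaction tests are not explicitly scheduled.

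The statistical cost is lost precision and no means of adjusting for chance imbalance in about 40 men, across 13 named blood analytes and, if they are not tested before the first serving, 6 reaction-test parameters. The documents give no correlation between baseline and later values, so the loss of precision cannot be sized. Separately, the data entering the section 11 ANOVA depend on which section is followed. The conflicts do not depend on any assumption; only the figure of 18 servings before day 1 does. This should be settled before the first serving is given.

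**What to change.** Replace the conflicting text with one schedule of assessments.

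1. The sponsor reconciles the supplementation period and the drink timing across sections 1, 2, 8, 9 and 10.3. This review takes no view on which is right.
2. State that the day-1 draw is taken before the first serving, and have section 11 use it as the biomarker baseline in the group comparison. If the reconciled period begins before day 1, that draw must be moved so that it precedes the first serving.
3. Give one time for the pre-exercise draw, and confirm or delete the 24 h draw.
4. Assign both reaction tests to named visits, including one before the first serving and one at a fixed point on day 11. State whether the psychological form is the section 10.6 questionnaire.
5. Name in section 11 the time points that enter the repeated-measures analysis.

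**Cost.** Mostly protocol text, using draws and tests already named. The reaction tests add time at the visits chosen; the documents give no duration. Confirming the 24 h draw adds one contact for each of about 40 men that sections 2 and 8 do not list, and deleting it loses the 24 h recovery measure. Moving the first draw, if needed, changes the visit calendar.

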10.6 Subjective analysis of fatigue

A questionnaire will be developed about the subjective perception of patients about the effects of the treatment employed in the recovery of muscle fatigue. The questions will be based on the Chalder scale and the International Short-Form Physical Activity Questionnaire (IPAQ-SF) (LEE et al., 2011). However, the feeling of improvement or not of physical fatigue after exercise will be the focus of the preparation of a new and unprecedented questionnaire

11. Statistical analysis

The results will be expressed as mean \pm SEM (standard error of the mean). Statistical analysis will be performed by one-way analysis of variance (ANOVA) (repeated measures), followed by Tukey's post hoc test, using the Prism software (Prism 6.0, GraphPad Software, Inc., San Diego, CA, USA). The differences will be considered significant when $p < 0.05$.

REFERENCES

ARCURI, J. F. et al. Validity and Reliability of the 6-Minute Step Test in Healthy Individuals: A Cross-sectional Study. **Clinical Journal of Sport Medicine**, v. 26, n. 1, p. 69-75, Jan. 2016.

BUTCHER, J. T. et al. Effect of myostatin deletion on cardiac and microvascular function. **Physiological Reports**, v. 5, n. 23, e13525, Dec. 2017.

CABARKAPA, D. et al. Position-specific differences in countermovement vertical jump force-time metrics in professional male basketball players. **Front Sports Act Living**, v. 20, n. 5, p. 1218234, Jul. 2023.

CARDOSO, A.L. et al. An Update on the Biological Activities of *Euterpe edulis* (Juçara). **Planta Médica**, v. 84, n. 8, p. 487-499, may., 2018.

CARROLL, T. J.; TAYLOR, J. L.; GANDEVIA, S. C. Recovery of central and peripheral neuromuscular fatigue after exercise. **Journal of Applied Physiology**, v. 122, n. 5, p. 1068-1076, May. 2017.

ELY, M. R. et al. A single dose of histamine-receptor antagonists before downhill running alters markers of muscle damage and delayed-onset muscle soreness. **Journal of Applied Physiology** v. 122, n. 3, p. 631-641, mar. 2017.

FANG, P. et al. Adipose-Muscle crosstalk in age-related metabolic disorders: The emerging roles of adipo-myokines. **Ageing Research Reviews**, v. 84, p. 101829, Feb. 2023.

FELZENSZWALB, I. et al. Toxicological evaluation of *Euterpe edulis*: a potential superfruit to be considered. **Food and Chemical Toxicology**, v. 58, p. 536-44, Aug. 2013.

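### Without a plasma-volume correction, the within-arm change from rest to 3 minutes after exercise mixes release with haemoconcentration; the juice-placebo comparison is largely protected

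*Combined protocol and SAP*

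**What the plan says.** Section 10.3 describes three draws. The first is at rest: "Blood samples will be collected 1 hour before the high-intensity strength exercise, in the condition of muscle rest". The second follows the exercise: "New blood samples will be collected after the completion of the muscular effort, specifically 3 minutes after the exercise performed". The third is described as "in addition to the 3rd sample after 24 hours of rest". CK, total antioxidant capacity, testosterone, cortisol and growth hormone are to be measured in plasma. The cytokines are measured in serum: "In addition to serum concentrations of inflammatory biomarkers such as interleukins (IL-6, IL-8, IL10) and TNF-alpha". On tubes the section says: "The samples will be stored in tubes containing ethylenediamine tetraacetic acid (EDTA) 10 or without anticoagulants".

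Section 11 reports mean and SEM and continues: "Statistical analysis will be performed by one-way analysis of variance (ANOVA) (repeated measures), followed by Tukey's post hoc test". It does not name the repeated factor, but time is the natural reading. It states no group-by-time term, no transformation and no adjustment of the measured values. Haematocrit, haemoglobin, plasma volume and posture at the draw are mentioned nowhere.

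Sections 2 and 8 give a different schedule. On D11 blood is drawn at time zero, the drink follows, the battery starts two hours later, and then: "At the end, the blood will be collected, and a psychological form will be applied". Section 2 adds a D1 draw. Neither section mentions 3 minutes or 24 hours.

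**The concern.** A concentration is an amount divided by a volume. If hard effort shifts fluid out of the circulation, a marker that stays in the plasma becomes more concentrated although none has been released. The 3-minute sample would carry this effect and the resting sample would not. The planned repeated-measures test looks directly at the difference between them. For markers that vary little within a man, a significant post-exercise rise could be wholly or partly haemoconcentration, and the planned measurements offer no way to tell. Once the blood has been spun and frozen, haematocrit cannot be recovered.

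**Working it through.** **Inputs from the documents.** Draw times and analytes are from section 10.3 and the model from section 11. Sections 1 to 3 give about 40 men, two randomised groups, 250 mL in each arm, alpha 0.05 and a calculated sample size of 20. The plan has no plasma-volume or biomarker figure to reproduce. It does not say whether the 20 is a total or a group size, and it gives no allocation ratio, so results are shown for 20 and for 10 men per arm.

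**Assumptions, not in the documents.** Plasma-volume loss L at the 3-minute draw is 5% to 20%. The SD of the within-man log change is 0.08 to 0.5, not tied to any particular marker. Tests are two-sided.

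**Step 1: apparent rise with no release.** The ratio of post-exercise to resting concentration is 1/(1 − L).

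| L | 1/(1 − L) | apparent rise |
|---|---|---|
| 5% | 1.053 | 5% |
| 10% | 1.111 | 11% |
| 15% | 1.176 | 18% |
| 20% | 1.250 | 25% |

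**Step 2: how often the within-arm change is significant.** For a paired t-test on log change, the noncentrality is −ln(1 − L) × √n / SD, with n − 1 degrees of freedom. At L = 10%, −ln(0.90) = 0.1054. With n = 20 and SD 0.15 this is 0.1054 × 4.472 / 0.15 = 3.14.

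| SD of log change | 20 men | 10 men |
|---|---|---|
| 0.15 | 85% | 51% |
| 0.25 | 43% | 22% |
| 0.5 | 15% | 9% |

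At SD 0.08 and 20 men it is about 100%.

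**Step 3: the planned test.** Step 2 is unadjusted, whereas section 11 uses Tukey after a repeated-measures ANOVA. I simulated that on the log scale with three times, a 10% loss at the middle time only, equal error variance and 20 men (20,000 trials). Tukey's contrast of rest with 3 minutes is significant in about 75%, 30% and 8% of trials at SD 0.15, 0.25 and 0.5. The adjustment lowers the rates but does not remove the effect at the smaller SDs.

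**Step 4: juice against placebo.** With equal losses the spurious arm ratio is (1 − L)/(1 − L) = 1.00 and rejection stays at 5%. A simulation of raw change with equal mean loss, 20 per arm, gave 4.8%. With unequal losses the log difference is ln[(1 − L₁)/(1 − L₂)], and the noncentrality is that difference divided by SD × √(2/n).

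| Losses | log difference | spurious ratio | rejection, 20 per arm, SD 0.08 / 0.15 / 0.25 / 0.5 |
|---|---|---|---|
| 10% v 11% | ln(0.90/0.89) = 0.0112 | 1.011 | 7.1% / 5.6% / 5.2% / 5.1% |
| 10% v 13% | ln(0.90/0.87) = 0.0339 | 1.034 | 26% / 11% / 7% / 5.5% |

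**The case against.** The strongest reply is that the trial exists to compare juice with control, and randomisation protects that comparison. Both arms face the same battery and the same fluid volume, so there is little reason to expect different losses. This stands. A reader might infer that haemoconcentration creates a false juice effect; the documents do not support that. It would need the arms to lose different volumes, for example because juice lets men work harder, and nothing in the documents shows that they will. One small qualification: on the raw scale an equal loss stretches a true 3-minute arm difference, so 10 units reads as 10/0.90 = 11.1 at a 10% loss.

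A reader might also infer that the plan treats any post-exercise rise as release. It does not say so. If plasma volume falls, the concentration really has changed, and a test on concentration that rejects is correct. The percentages in step 2 are therefore not false-positive rates for the quantity measured. They become error rates only if a rise is reported as release.

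Three further points carry weight:

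- The loss and the SDs are assumed, and at SD 0.5 the effect is modest.
- Section 10.3 takes its collection method from a cited trial that cannot be seen here, so uncorrected analysis is inferred from silence. Even so, the listed measurements would not permit a correction.
- The 3-minute timing appears only in section 10.3, and the size of the effect depends on it. Sections 2 and 8 also place a draw at the end of the battery, so the question arises under either schedule.

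**Conclusion.** The point holds as a limited one about measurement. As planned, the within-arm change from rest to 3 minutes cannot separate release from haemoconcentration. With no release, the apparent rise is 5% to 25% for assumed losses of 5% to 20%. Whether that produces a significant result depends on the marker: likely at a log-change SD of 0.15 with 20 men, uncommon at 0.5, and less frequent throughout with 10 men. The between-arm comparison stays at or near 5% unless losses differ. A one-point difference (10% v 11%) barely moves it, and 10% v 13% matters mainly for the least variable markers.

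All of this assumes that plasma volume is reduced at the 3-minute draw and that the marker stays in the plasma. The absence of a group-by-time term adds to the problem, because the written analysis then leans on the confounded within-arm change. This is a cheap improvement worth making before the first draw; it does not invalidate the trial.

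**What to change.** 1. Reconcile the blood-draw schedules in sections 2, 8 and 10.3, so that the resting, post-exercise and any 24-hour samples are defined once.
2. In section 10.3, provide an EDTA tube at every draw and read haematocrit (Hct) and haemoglobin (Hb) from it before centrifugation. Standardise posture at the draw.
3. For each man compute R = (Hb at rest / Hb at time t) × (1 − Hct at time t) / (1 − Hct at rest), which assumes that circulating haemoglobin mass is unchanged between draws. Corrected concentration = measured concentration × R. Report corrected beside uncorrected values for the 3-minute and 24-hour samples.
4. In section 11, state that a within-arm post-exercise rise is called a release or response only if it persists after correction. State also that juice effects rest on the between-arm comparison of change (group by time, or baseline-adjusted).

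The cost is two routine readings per draw and one derived variable, with no additional draw or participant. The downside is that error in the readings adds slightly to the variance of the corrected values.

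### Section 11 names no transformation, so CK and the cytokines default to a raw-scale ANOVA that loses power if they vary multiplicatively; the scale should be prespecified marker by marker

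*Combined protocol and SAP*

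**What the plan says.** Section 10.3 lists the blood outcomes: lactate, then "In plasma, creatine kinase (CK), total antioxidant capacity (TAC) and concentrations of testosterone (T), cortisol", growth hormone, and serum IL-6, IL-8, IL-10 and TNF-alpha. An earlier paragraph of that section gives a different inflammatory list, which adds IL-1 beta, monocyte chemoattractant protein 1, adhesion molecules and adiponectin. Sampling is before exercise, 3 minutes after it and 24 hours after it.

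Section 11 has one rule for everything. Results are summarised as mean and SEM, and "Statistical analysis will be performed by one-way analysis of variance (ANOVA) (repeated measures), followed by Tukey's post hoc test", with significance at p < 0.05. The section mentions no log scale, geometric mean, distribution check, rank-based fallback or rule for values below the detection limit.

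On size, Section 1 says "There will be about 40 men, aged 19 to 30 years", and Section 3 says "the value of 20 patients was reached" without saying whether that is the total or the number per group. No effect size, SD or CV is given for any marker, and no primary endpoint is named.

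**The concern.** CK and cytokine concentrations are positive quantities measured around a hard bout of exercise. If men differ, and respond, by factors rather than by fixed amounts, the spread grows with the level and the upper tail is long. The arithmetic mean and its SEM then depend heavily on the highest values, and the equal-variance normal model behind ANOVA fits poorly.

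Two things would be at stake. The first is power to see a juice effect on the muscle-damage and inflammation markers in a trial of about 40 men. The second is the error rate at the exercise peak: an error term averaged over quiet and peak times is too small for the peak. With no scale fixed in advance, the choice could also be made after the data are seen.

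**Working it through.** **Inputs.** Two groups (Section 2: "The men will be randomized into two groups, called GJ who will receive the sample and GP who will receive the placebo"). About 40 men, so 40/2 = 20 per arm if allocation is 1:1, which is not stated. Two-sided alpha 0.05 (Section 3 gives 0.05 but not the sidedness). All measures of spread below are assumptions.

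**The plan's own figure.** The 20 patients in Section 3 cannot be reproduced, because no effect size is given. Solved backwards for a two-sided two-sample t-test at 95% power, 20 corresponds to d = 1.17 if per arm and d = 1.71 if in total. Neither value says anything about scale.

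**Step 1: one time point, multiplicative variation.** Log-normal values, 20 per arm, true effect 0.91 log-SD (80% power on the log scale), two-sample t-test on raw and on log values, 20,000 simulated trials per row. CV = √(exp(s²) − 1), where s is the log-SD. For small effects, the raw scale needs (exp(s²) − 1)/s² times the sample size.

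| log-SD | CV | Size factor | Raw power | Log power | Raw type I error |
|---|---|---|---|---|---|
| 0.3 | 31% | 1.05 | 78.5% | 80.1% | 4.6% |
| 0.5 | 53% | 1.14 | 75.7% | 80.3% | 4.8% |
| 0.8 | 95% | 1.40 | 67.5% | 79.7% | 4.2% |
| 1.0 | 131% | 1.72 | 61.1% | 80.2% | 3.7% |
| 1.2 | 179% | 2.24 | 52.7% | 79.7% | 3.5% |

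A separate run indexed by CV agrees: raw power 79%, 78%, 76%, 70%, 67% and 58% at CV 20%, 30%, 50%, 80%, 100% and 150%. At 10 per arm the last figure is 53%.

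**Step 2: with baseline adjustment.** 20 per arm, two-fold exercise rise, group plus baseline value in the model. Raw against log power is 78/80%, 76/80%, 70/80% and 58/80% at between-/within-man log-SD 0.2/0.15, 0.3/0.2, 0.5/0.25 and 0.8/0.3.

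**Step 3: error pooled over times.** Assume no juice effect, a proportional rise by a factor f at the peak, and a return to the starting level by the third sample. The SD is then proportional to 1, f, 1. The peak variance relative to the pooled variance is f² ÷ [(1 + f² + 1)/3] = 3f²/(2 + f²). An unadjusted 5% test at the peak rejects at about 2[1 − Φ(1.96/√ratio)].

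- f = 2: ratio 12/6 = 2; 1.96/1.414 = 1.39; rejection about 17%.
- f = 4: ratio 48/18 = 2.67; 1.96/1.633 = 1.20; rejection about 23%.

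If the third sample is still raised, say at 1.5 and 2 times the start, the ratios are 4/2.417 = 1.66 and 16/7 = 2.29, and the rates about 13% and 20%. Simulations of this setting gave about 13% to 24% on the raw scale and about 5% on the log scale. With Tukey over the six group-by-time cells, the per-contrast rate was about 0.5% on the log scale and 2-3% (f = 2) or 5-6% (f = 4) on the raw scale.

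**Step 4: the reverse case.** A normal marker with an additive downward effect and 80% raw power at 20 per arm has log-scale power of 80%, 79%, 74% and 68% at CV 10%, 20%, 30% and 40%. For an upward effect, log power is 78% at CV 30% and 74% at CV 40%.

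**Step 5: undetectable values.** With log-SD 0.5, the same 0.91 SD effect and 30% of placebo values undetectable, log power is 77% if LOD/2 is substituted, 68% with LOD/10 and 60% with LOD/100. Raw power stays at 76-77%. At log-SD 1.0 the log scale stays ahead under each of these rules.

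**The case against.** The strongest reply is that Steps 1 to 3 build in multiplicative variation, and the documents offer no evidence for it. That stands: every size here is conditional. At a CV of about 30% or less, the single-time loss is at most about 2 points.

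A reader might infer that the log scale is at least as good for every marker and costs nothing. Step 4 refutes the first part. For simple pre-to-post changes with small variation the raw scale can also lead, with 85% and 82% against 80% at between-/within-man log-SD 0.2/0.15 and 0.3/0.2. Step 5 refutes the second: the benefit can disappear under a poor substitution rule, and the effect measure becomes a ratio.

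A reader might also infer that the plan expressly chooses the raw scale. It does not; the raw scale follows from silence together with arithmetic means. Nor does the plan say how the ANOVA error is formed, so Step 3 is a warning about a common form of the analysis, not a finding about a stated one.

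Finally, it can be said that the raw test is conservative and so safe. That holds for the single-time comparison (3.5-4.8%), but not for a pooled-error ANOVA at the peak. With no primary endpoint named, these markers cannot be shown to carry the trial's main conclusion, which limits the weight of the point.

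**Conclusion.** The point holds as a cheap improvement, not as a flaw that invalidates the analysis. By plain reading, CK and the cytokines would be analysed untransformed. If they vary multiplicatively, with 20 men per arm, the single-time loss against 80% power runs from about 1 or 2 points at log-SD 0.3 to about 12 at 0.8 and 27 at 1.2. If the error is pooled over times and the rise is proportional, unadjusted false positives at the peak are about 13-24% instead of 5%.

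The documents do not support a claim that this trial will lose a particular amount of power, because they give no CV. They also do not support a log scale for all the listed markers: no case is made for TAC, testosterone or cortisol. Two neighbouring gaps are larger and separate: a one-way repeated-measures ANOVA does not in itself specify the juice-placebo contrast, and the sample size has no stated effect size.

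**What to change.** Amend Section 11, before unblinding, as follows.

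- Natural-log transform CK, the cytokines (named in one agreed list, since Section 10.3 gives two) and other markers expected to rise proportionally, for example growth hormone and lactate.
- At each post-exercise time, compare juice with placebo by a model with group and the log baseline value. Report the ratio of geometric means with 95% CI.
- Name the baseline sample. The documents describe a D1 sample, a D11 sample at time zero (Section 2) and a sample 1 hour before exercise (Section 10.3), and these descriptions need reconciling. A D11 sample follows ten days of product, so adjusting for it answers a different question from adjusting for D1.
- State a detection-limit rule, for example LOD/2, with a sensitivity check.
- Keep TAC, testosterone and cortisol on the raw scale, also baseline-adjusted, unless a log scale is justified for that marker.

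The cost is a few sentences and no extra men or samples. The downside is that effects are read as ratios, undetectable values need substitution, and some power is lost for any logged marker that is in fact additive.
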